9.1.4 Clinical Laboratory Changes

Any abnormality in a laboratory value that is new in onset or which has worsened in severity or frequency from the Baseline condition and meets 1 of the following criteria will be recorded on the AE pages of the eCRF:

- Requires therapeutic intervention or diagnostic tests
- Leads to discontinuation of study drug
- Has accompanying or inducing symptoms or signs
- Is judged by the Investigator as clinically significant

Combined elevations of aminotransferases and bilirubin, either serious or nonserious, and whether or not causally related, meeting the criteria of a potential Hy's Law case (total bilirubin level $\geq 2 \times \text{ULN}$) with simultaneously ALT or AST $\geq 3 \times \text{ULN}$) should always be reported to the Sponsor as soon as possible following the procedures outlined in Section 9.2.2 for SAE reporting, with the Investigator's assessment of seriousness, causality, and a detailed narrative.

Confidential Page 74 of 102

9.1.5 Assessment of Severity

Each AE will be classified according to the following criteria:

Mild: The AE does not interfere in a significant manner with the patient's

normal level of functioning.

Moderate: The AE produces some impairment of functioning, but is not

hazardous to the patient's health.

Severe: The AE produces significant impairment of functioning or

incapacitation and is a definite hazard to the patient's health.

Severity versus Seriousness: Severity is used to describe the intensity of a specific event while the event itself may be of relatively minor medical significance (such as severe headache). Severity is not the same as "seriousness," which is based on patient/event outcome at the time of the event.

When changes in the severity of an AE occur more frequently than once a day, the maximum severity for the experience should be noted. If the severity category changes over several days, those changes should be recorded as separate AEs (with distinct onset dates).

9.1.6 Assessment of Relationship

Each AE will be assessed as to its relationship to the study drug, based on the following criteria. Although the attribution by the Investigator will be collected for reported events, for analytic purposes a temporal association with the use of the study drug will be assumed sufficient for at least plausible association.

Not related: No causal relationship exists between the study drug and the AE, but

an obvious alternative cause exists, e.g., the patient's underlying

medical condition or concomitant therapy.

Possibly related: A connection with the administration of the study drug appears

unlikely, but cannot be ruled out with certainty. An AE may be considered possibly related if or when it meets 2 of the following

criteria: (1) it follows a reasonable temporal sequence from

administration of the study drug; (2) it could not readily have been produced by the patient's clinical state, environmental or toxic factors, or other modes of therapy administered to the patient; or (3) it follows a known pattern of response to the study drug.

Related: There is a reasonable/plausible possibility that the AE may have been

caused by the study drug.

When assessing the relationship to the study drug, the following criteria will be considered:

Positive rechallenge

• Positive dechallenge (resolution upon stopping the suspect study drug, in absence of other intervention or treatment)

Confidential Page 75 of 102

- Known class effect
- Biological plausibility
- Lack of alternative explanation (e.g., a concomitant drug or disease)

9.1.7 Action Taken Regarding Study Drug

The action taken regarding the study drug as a result of an AE should be selected from 1 of the categories listed below and recorded in the eCRF:

- Dose Not Changed: No change in study drug dose was made.
- Drug Interrupted: The study drug was temporarily stopped.
- Drug Withdrawn: The study drug was permanently stopped.
- Not Applicable: Patient died, study treatment had been completed prior to reaction/event, or reaction/event occurred prior to the start of treatment.
- Unknown.

9.1.8 Other Action Taken for Event

Other action(s) taken as a result of the AE should be selected from 1 of the categories listed below and recorded in the eCRF:

- None (i.e., no treatment was required)
- Therapy(ies) required (i.e., prescription and/or OTC medication was required to treat the AE)
- Hospitalization or prolongation of hospitalization required (i.e., hospitalization was required or prolonged because of the AE, whether medication was required)
- Other

9.1.9 Adverse Event Outcome

The outcome of the AE should be selected from 1 of the categories listed below and recorded in the eCRF:

- Recovered/Resolved (i.e., the patient fully recovered from the AE with no residual effect observed)
- Recovering/Resolving (i.e., the AE improved but has not fully resolved)
- Not Recovered/Not Resolved (i.e., the AE is still present and observable)

Confidential Page 76 of 102

- Recovered/Resolved with Sequelae (i.e., the residual effects of the AE are still present and observable, including sequelae/residual effects)
- Fatal (i.e., "fatal" should be used when death is a direct outcome of the AE)
- Unknown

9.2 Reporting Procedures and Requirements

9.2.1 Adverse Events

Each time the patient is seen or contacted by the Investigator or the study staff, be it at the study clinic, hospital, or over the telephone, the Investigator will determine whether any AE has occurred by evaluating the patient. AEs may be directly observed, reported spontaneously by the patient, or by questioning the patient at each contact. Patients should be questioned in a general way, without asking about the occurrence of any specific symptoms. If AEs occur, the first concern will be the safety of the study patients. All AEs will be followed until resolved or stable and the outcome documented in the patient's source documentation/medical record, and in the eCRF.

Any AE that occurs after the patient signs the ICF until 14 days after the end of the Treatment Period will be recorded in the patient's source documentation/medical record and on the AE page of the eCRF. If the Investigator detects an AE in a patient after the last scheduled study visit and considers the event possibly related or related to prior study treatment, the Investigator should report it to the Sponsor or designated representative.

Illnesses that are present at the time informed consent is given are to be regarded as concomitant illnesses and recorded in the medical history. Investigators should document all significant illnesses that the patient has experienced within 30 days of Screening as a prior illness. Illnesses first occurring or detected during the study and/or worsening of a concomitant illness during the study are to be documented as AEs.

All clinical laboratory results, vital signs, and ECG results or findings should be evaluated by the Investigator to determine their clinical significance. Isolated abnormal clinical laboratory test results, vital sign findings, or ECG findings (i.e., not part of a reported diagnosis) should be reported as AEs if they are symptomatic, lead to study drug discontinuation or dose reduction, require corrective treatment, or constitute an AE in the Investigator's clinical judgment.

9.2.2 Serious Adverse Events

Each AE will be assessed to determine whether it meets seriousness criteria (Section 9.1.2). If the AE is considered serious, the Investigator should report this even to the IRB according to its standard operating procedures (SOPs).

If the Investigator detects an SAE in a study patient after the last scheduled study visit, and considers the SAE related or possibly related to this study's study drug administration, the Investigator should report it to Sponsor or designated representative.

Confidential Page 77 of 102

The Investigator must report all SAEs on the eCRF page within 24 hours of learning about the event regardless of relationship to study drug. If the site experiences a temporary disruption of the eCRF system, a back-up paper SAE Report Form will be available for site staff to complete.

At minimum, the initial report of the SAE should include the following information:

- AE description
- Study code/protocol number
- Patient number and year of birth
- Study drug
- Reporter name and contact information
- Relationship to the study drug

If the eCRF system is not available, the site staff will complete the back-up paper SAE Report Form and e-mail it within 24 hours to the following address: [contact].

In cases where the email system is unavailable, site staff will transmit the back-up paper SAE Report Form by fax to

If notification is made via email or fax, site staff must enter the SAE information into the eCRF system as soon as the system becomes available. The original paper SAE Report Form submitted should be kept at the study site with the patient's source documentation/medical record or in the site's study files.

If the SAE has not resolved at the time the Investigator submits an initial SAE report, the Investigator must provide a follow-up report as soon as the event resolves (or upon receipt of significant information if the event is still ongoing). Additional follow-up information must be reported in the eCRF within 24 hours of awareness following Investigator (or site) awareness of the information. The Investigator should not delay reporting an SAE in order to obtain additional information. Additional information, when available, should be reported per the reporting procedures described above.

All SAEs shall be followed until resolution, until the condition stabilizes, or until the patient is lost to follow-up, or otherwise explained. Once the SAE is resolved, the corresponding AE eCRF page shall be updated. Additionally, any relevant laboratory test reports, consultation reports from other health care professionals, discharge summaries, or other information that has been gathered about the event shall be transmitted to the Sponsor and maintained in the patient's source documentation/medical record.

In the case of a "minimum report" (one that solely comprises the information bulleted above), a more detailed follow-up report should be sent as soon as more information becomes available but no later than 7 calendar days after the date of the initial report. For reported deaths, the Investigator should supply the IRB with any additional requested information

Confidential Page 78 of 102

(e.g., autopsy reports and terminal medical reports). Additionally, any such reports shall be maintained in the patient's source documentation/medical record.

The Sponsor or its representative will be responsible for determining and in turn, reporting SAEs to regulatory authorities according to the applicable regulatory requirements.

Any suspected unexpected serious adverse reaction must be reported according to applicable regulatory requirements.

9.2.3 Pregnancy During the Study

If a patient, or the female partner of a male patient, becomes pregnant during the study, the Investigator will notify the Sponsor or designated representative immediately after the pregnancy is confirmed. The Investigator will report any pregnancies using the eCRF Pregnancy Reporting Form within 24 hours of becoming aware of the event. The Investigator will also (1) notify the patient's physician that the patient was being treated with LB-102, and (2) follow the progress of the pregnancy and document the outcome of the pregnancy. Pregnancy outcome information should be forwarded to Sponsor or designated representative when available.

Patients who become pregnant during the study will not be eligible for any further study treatments, the study drug will be discontinued immediately, and the patient will complete an ET Visit. The Investigator should make every effort to follow the patient until completion of the pregnancy and complete the Exposure in Utero (EIU) Reporting Form eCRF with complete pregnancy outcome information, including normal delivery and induced abortion. Any adverse pregnancy outcome, either serious or nonserious, should be reported in accordance with study procedures. If the outcome of the pregnancy meets the criteria for immediate classification as an SAE (i.e., post-partum complications, spontaneous or induced abortion, stillbirth, neonatal death, or congenital anomaly, including that of an aborted fetus), the Investigator should follow the procedures for reporting SAEs outlined in Section 9.2.2. In the event the eCRF system is unavailable, a back-up paper Pregnancy Reporting Form will be available for site staff to complete following the reporting guidelines as outlined in Section 9.2.2.

For reports of pregnancy in the female partner of a male patient, the eCRF Pregnancy Report Form and EIU Reporting form (or SAE form if applicable) should be completed with the patient's identification number and year of birth, and details regarding the female partner should be entered in the narrative section. The pregnancy outcome of the female partner should be followed and the reporting procedures outlined above (for pregnant patients) should be followed; however, consent should be received prior to the collection of any information via a pregnant partner ICF. The male partner may continue in the study after re-education and confirmation that recommended birth control methods per exclusion criteria are being used.

Confidential Page 79 of 102

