1.8 Risks and Benefits for Patients

1.8.1 **Risks**

Administration of second generation antipsychotics (SGAs) (including the metabolite of LB-102, can result in extrapyramidal symptoms, weight gain, elevations in lipids and blood sugar, sedation, dry mouth, constipation, dizziness, and falls due to low blood pressure, QTcF prolongation, cognitive impairment, and prolactin elevation.¹

Electrocardiograms (ECGs) and clinical laboratory tests will be conducted throughout the study.

The effect of LB-102 on pregnant women and fetal development is unknown. Therefore, women who are pregnant or lactating will be excluded from this study, and highly effective contraception will be required of all female participants of childbearing potential and of male participants with sexual partners of childbearing potential. Pregnancy tests will also be required of female participants of childbearing potential before the start of treatment.

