4.2 Study Duration

The duration of participation for each individual patient in this study will be approximately 8 weeks, including a 7-day inpatient screening phase (up to a 7-day extension of the screening phase is allowed, if necessary with the approval of the Medical Monitor), a 28-day inpatient Study Treatment Period and up to 5-day inpatient Stabilization Period, and the Final Safety Follow-up approximately 2 weeks after the completion of the Treatment Period.

sites are planned to randomly assign patients over a 18-month period.

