6.7.1 Acceptable Contraceptive Methods

For females of childbearing potential who may participate in the study, the following methods of contraception, if used properly and used for the duration of the study and for 30 days after the last dose of study medication, are generally considered reliable; however, if employing birth control, each couple must use 2 of the following precautions: oral contraceptives, patch contraceptives, injection contraceptives, implantable hormonal contraceptives, male condom with intravaginal spermicide, diaphragm or cervical cap with spermicide, vaginal contraceptive ring, intrauterine device or system, surgical sterilization (hysterectomy, bilateral oophorectomy, and/or bilateral salpingectomy), tubal ligation/occlusion, vasectomized partner, or sexual abstinence, if this is the patient's current practice. Contraceptive requirements do not apply to patients who are in same sex relationship, who are medically or surgically sterilized (e.g., bilateral tubal ligation, bilateral oophorectomy, hysterectomy); or practice sexual abstinence during this study.

These methods of contraception also apply to female partners of male patients.

The Investigator and each patient will determine the appropriate method of contraception for the patient during participation in the study. This will be documented at the Screening Visit in the patient's source documentation/medical record.

Male patients or male partners of female patients should not donate sperm until 90 calendar days after the last dose of study drug.

Confidential Page 52 of 102

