7.2.10 Visit 6 (Study Day 28)

On Study Day 28, all assessments should be performed on the same day; the last day of study drug dosing is Day 28 and, if possible, when any patient discontinues prior to this visit, the following assessments will be performed:

• Recording of concomitant medications (e.g., prescription and nonprescription medications)

Confidential Page 62 of 102

- Full physical examination (if applicable)
- Bodyweight, BMI (derived programmatically from body weight and height measurements), and waist circumference
- Vital signs
- Resting 12-lead ECG (triplicate, further information in Section 8.2.3)
- Collection of blood and urine samples for clinical laboratory tests. Additional information is presented in the footnotes to the SoA (Table)
- Study drug administration
- Urine pregnancy test for all females of childbearing potential
- Assessment and recording of AEs
- PANSS. PCRS must be administered before PANSS
- CGI-S
- C-SSRS
- AIMS, 3 to 6 hours post-dose
- BARS, 3 to 6 hours post-dose
- SAS, 3 to 6 hours post-dose
- Cogstate test

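### The pregnancy-reporting trigger ends with the study (about Day 42), some 16 days before the protocol's own contraception period does

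*Protocol*

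**What the plan says.** Protocol Section 9.2.3 opens with the trigger: "If a patient, or the female partner of a male patient, becomes pregnant during the study, the Investigator will notify the Sponsor". It names no period after the last dose. A later sentence is broader: "The Investigator will report any pregnancies using the eCRF Pregnancy Reporting Form within 24 hours of becoming aware of the event".

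Section 5.3 treats a patient as having completed the study at the End of Study visit, which Section 7.1 places on Day 42 ± 2. Section 4.2 describes this as the "Final Safety Follow-up approximately 2 weeks after the completion of the Treatment Period". Section 7.2.10 states that "the last day of study drug dosing is Day 28".

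The contraception requirement runs longer. Exclusion criterion 1 sets 30 days after the last dose for women of childbearing potential and for men. Section 6.7.1 says its methods are reliable "if used properly and used for the duration of the study and for 30 days after the last dose of study medication" and extends them to female partners of male patients. The same section has a separate donation rule: "Male patients or male partners of female patients should not donate sperm until 90 calendar days after the last dose of study drug".

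Scheduled pregnancy tests are at Screening, Day 1, Day 28 or early termination (ET), and Day 33 or the last stabilization day (Sections 7.1, 7.2.12). The End of Study visit has none (Section 7.2.13), and no contact is scheduled after it. Section 1.8.1 says: "The effect of LB-102 on pregnant women and fetal development is unknown". SAP Section 5.13.11 only lists pregnancy test results.

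**The concern.** The protocol asks patients and partners to avoid conception for 30 days after dosing, but its rule for reporting a pregnancy is tied to the study, which ends for a completer about 14 days after dosing. Patients are inpatients until stabilization ends, Day 33 at the latest. In completers, conceptions within the contraception period are therefore possible mainly in the outpatient days, and more than half of those days fall after the study at the nominal schedule.

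What is at stake is systematic safety capture. The drug's fetal effect is stated to be unknown. A pregnancy that began within the contraception period but after the last visit would reach the sponsor only if someone happened to tell the site. A report of few or no pregnancies would then partly reflect how long anyone was asked.

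**Working it through.** This is day arithmetic.

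**Inputs**
- Last dose: Day 28 (Section 7.2.10).
- End of Study: Day 42 ± 2, so Days 40 to 44 (Section 7.1).
- Contraception: 30 days after the last dose (exclusion criterion 1; Section 6.7.1).
- Discharge: end of stabilization, which lasts up to 5 days, Days 29 to 33 (Section 7.1). I vary it from Day 28 (no stabilization) to Day 33.

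**Plan's own figure.** Day 28 + 14 = Day 42, which reproduces the stated End of Study day.

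**Days outside the trigger, completer**
- Contraception ends on Day 28 + 30 = Day 58.
- Uncovered days = 58 − End of Study day: 58 − 42 = 16; range 58 − 44 = 14 to 58 − 40 = 18.
- Share of all post-dose days at the nominal visit: 16/30 = 53%.

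**Share of outpatient days** = (58 − End of Study day) / (58 − discharge day). Nominal case: (58 − 42) / (58 − 33) = 16/25 = 64%.

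| Discharge | End of Study Day 40 | Day 42 | Day 44 |
|---|---|---|---|
| Day 28 | 18/30 = 60.0% | 16/30 = 53.3% | 14/30 = 46.7% |
| Day 29 | 18/29 = 62.1% | 16/29 = 55.2% | 14/29 = 48.3% |
| Day 31 | 18/27 = 66.7% | 16/27 = 59.3% | 14/27 = 51.9% |
| Day 33 | 18/25 = 72.0% | 16/25 = 64.0% | 14/25 = 56.0% |

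The range is 47% to 72%. It drops below half only when discharge on Day 28 or 29 meets a Day 44 visit.

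**Early terminators.** Section 8.2 places the final assessment at Day 42 or at discontinuation, and Sections 5.3 and 7.2.14 set no visit after ET. If the ET visit is k days after the last dose, 30 − k days are uncovered. The documents do not give k; if the visit follows soon after the last dose, this is most of the 30 days. The sample-size section assumes 25% drop-out, so the group is not marginal.

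**Testing.** In a completer, every scheduled test falls before outpatient time begins. Even a conception on Days 34 to 42, which is within the trigger, would be found only by an unscheduled test or because the patient says so.

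**Exposure by then.** Section 7.2.12 expects LB-102 and its metabolites to be minimal within 5 days of the end of treatment, about Day 33. Mean single-dose half-lives in Table 14.1 run from 11.933 to 14.146 hours. Day 43 is 15 days, or 360 hours, after the last dose: 360 / 14.146 ≈ 25 half-lives.

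**The case against.** The strongest objection concerns exposure. The protocol never calls the 30 days an exposure window; it is a contraception precaution. By the protocol's own account the drug is nearly gone by about Day 33, so Days 43 to 58 are the least exposed part of the period. This stands for completers. A reader might infer that exposed pregnancies would be hidden, and the documents do not support that for completers. It carries less weight for early terminators, whose uncovered days can begin soon after the last dose.

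Second, reporting is not barred. The 24-hour sentence covers any pregnancy and has no end date of its own. Section 9.2.3 routes outcomes such as stillbirth and congenital anomaly to serious adverse event reporting, and Sections 9.1.2 and 9.2.2 keep related serious events reportable after the study. This stands too, so it would be wrong to say that later pregnancies cannot be reported. But the 24-hour sentence sits under a heading limited to the study, and all these routes depend on the site hearing of the event.

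Third, a reader might count the 90-day limit as a conception window and find 76 of 90 days (84%) uncovered. That does not follow: the limit governs sperm donation, and contraception for male patients is set at 30 days. The two rules cover different acts and do not contradict each other, although no reason is given for the difference.

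Finally, the consent form is not among the documents, so patients may already be asked to report later pregnancies.

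**Conclusion.** The mismatch is real but modest. About 16 days (14 to 18) of a completer's contraception period fall outside the Section 9.2.3 trigger, which is 64% of outpatient days at the nominal schedule and 47% to 72% over discharge and visit timing. For early terminators it may be most of the 30 days, nearer to dosing, and that is where the point matters most.

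This rests on two assumptions. One is that the study ends for reporting purposes at the End of Study or ET visit, since Section 9.2.3 does not define its own period. The other, needed to read the day shares as shares of conceptions, is uniform risk over outpatient days; the documents give no conception rate. The expected number of pregnancies is not stated and is probably small.

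The conclusion is limited to weak systematic capture of later pregnancies. It does not extend to a prohibition on reporting, or to material exposure going unseen in completers. No efficacy analysis is affected. This is an inexpensive improvement to safety reporting.

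**What to change.** Reconcile Section 9.2.3 with the post-dose contraception period in exclusion criterion 1 and Section 6.7.1, so that pregnancies in patients and partners are reportable from consent through the end of that period. Two points of wording matter:

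- Start at consent. Starting at first dose would drop a conception between consent and dosing that an early urine test could miss.
- Name the contraception period itself. A general reference to the post-dose window in Section 6.7.1 would be ambiguous, because that section holds both a 30-day and a 90-day figure.

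At Day 42 or the ET visit, ask patients to tell the site of any pregnancy in that period. State the reason for the differing 30-day and 90-day provisions for men, or reconcile them. While editing, settle the visit number: the End of Study visit is Visit 7 in Sections 5.3, 7.1 and 8.2 but Visit 8 in Table 7.1 and Section 7.2.13.

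The cost is protocol text, one instruction at the last visit, and consent wording if it does not already say this. No visit or test is added, and the existing pregnancy form, exposure-in-utero form and partner consent are used. The downside is a few late passive reports to follow up.
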